### 7.5.9. Composite WR, WIN and Pure Tone Audiometry Endpoint

- *Computation of the Endpoint*

The composite endpoint will be assessed in treated ears and defined as simultaneously meeting both of the following conditions at any visit (Day 90 or 210):

- A post-baseline  $\geq 10\%$  WR improvement OR a  $\geq 10\%$  WIN improvement, and
- A post-baseline 10 dB improvement in 2 contiguous frequencies or a post-baseline 15 dB improvement in any frequency for AC thresholds

Post-baseline  $\geq 10\%$  WR improvement is defined in Section 7.3.5 and  $\geq 10\%$  WIN improvement is defined in Section 7.4.5. Post-baseline  $\geq 10$  dB improvement in 2 contiguous frequencies for AC thresholds is defined in Section 7.5.2 and post-baseline  $\geq 15$  dB in any frequency for AC thresholds is defined in Section 7.5.3.

The composite endpoint will be computed as 1 if both conditions are met in the treated ear at the same visit for any of the post-baseline visits (Day 90 and 210) and as 0, otherwise.

- *Analysis of the Endpoint*

The incidence of the composite WR, WIN and pure tone audiometry endpoint for treated ears will be summarized using frequencies and percentages by treatment group for subjects in the FAS.

In treated ears only for subjects in the FAS, treatment group comparisons for the composite endpoint will be analyzed using a logistic regression model. The fixed covariates will include treatment group, WR score at baseline ( $< 50\%$  versus  $\geq 50\%$ ), and etiology of hearing loss (SSNHL versus NIHL). The treatment group differences analyzed will be between each FX-322 group (including the pooled FX-322 group) versus placebo, and comparisons between the individual FX-322 groups (excluding the pooled FX-322 group). Odds ratios, their 95% CIs, and p-values will be reported.

- *Sensitivity Analyses of the Endpoint*

The analyses will be repeated for subjects in the PPAS.

### 7.6. Extended High Frequency Audiometry

EHFA will be performed to determine a subject's threshold dB for hearing at frequencies beyond those in standard pure tone audiometry. Over-air frequencies used (no bone testing) are 9, 10, 11.2, 12.4, 14, and 16 kHz. If both masked and unmasked results are available for the same visit, date, ear, and frequency, the masked results will be used for analysis. This test will be performed at Screening, Day 15, 60, 90, 150, and 210.

Baseline scores for analysis will be computed from the Screening visit. For measurements post-Screening, missing response values for a given frequency with classification of "NR" (no

response due to subject audiometric thresholds greater than the maximal calibrated dB of the equipment), will be imputed using the maximum dB for the audiometry equipment of a given site plus 5 dB and classified as no signal at that frequency. Missing response values at Screening will remain missing.

#### 7.6.1. Air audiometry dB hearing thresholds by frequency

- *Computation of the Endpoint*

At each visit and by ear (left, right), the AC audiometry dB hearing thresholds will be recorded for each frequency (9, 10, 11.2, 12.4, 14, and 16 kHz). Left and right ears will be mapped to treated and untreated for analysis, as described in Section 3. Missing values will be imputed per Section 7.6.

- *Analysis of the Endpoint*

Descriptive summaries, treatment group comparisons, and the scatter plot will be performed for AC audiometry dB hearing thresholds as described in Section 7.5.1.

- *Sensitivity Analyses of the Endpoint*

The analyses will be repeated for subjects in the PPAS.

If there are any dosing administrations errors such that a not qualified ear is treated, the descriptive summaries by treated and untreated ears will be repeated for subjects in the FAS including all treated and untreated ear data.

#### 7.6.2. AC Improvement $\geq 10$ dB from baseline for two contiguous frequencies

- *Computation of the Endpoint*

AC Improvement  $\geq 10$  dB from baseline for two contiguous frequencies at each post-baseline visit for treated ears will be computed as 1 if the post-baseline threshold – baseline threshold is  $\geq 10$  dB for two contiguous frequencies and as 0, otherwise. The endpoint will utilize imputed values per Section 7.6.

- *Analysis of the Endpoint*

Descriptive summaries and treatment group comparisons may be performed for AC improvement  $\geq 10$  dB from baseline for two contiguous frequencies as described in Section 7.5.2.

- *Sensitivity Analyses of the Endpoint*

The analyses will be repeated for subjects in the PPAS.

#### 7.6.3. AC Improvement $\geq 15$ dB from baseline for any frequency

- *Computation of the Endpoint*

AC Improvement  $\geq 15$  dB from baseline for any frequency at each post-baseline visit for treated ears will be computed as 1 if the post-baseline threshold – baseline threshold is  $\geq 15$  dB for any frequency and as 0, otherwise. The endpoint will utilize imputed values per Section 7.6.

- *Analysis of the Endpoint*

Descriptive summaries and treatment group comparisons may be performed for AC improvement  $\geq 15$  dB from baseline for any frequency as described in Section 7.5.3.

- *Sensitivity Analyses of the Endpoint*

The analyses will be repeated for subjects in the PPAS.

#### 7.6.4. AC Composite Improvement

- *Computation of the Endpoint*

The AC Composite Improvement endpoint is defined as the occurrence of either or both of the following conditions for a given subject's ear for a given visit: 1) AC Improvement  $\geq 10$  dB from baseline for two contiguous frequencies as described in Section 7.6.2 or 2) AC improvement  $\geq 15$  dB from baseline for any frequency as defined in Section 7.6.3.

- *Analysis of the Endpoint*

The incidence of AC Composite Improvement at each post-baseline visit for treated ears will be summarized using the approach described in Section 7.6.2 for subjects in the FAS.

Descriptive summaries and treatment group comparisons may be performed for AC Composite Improvement as described in Section 7.5.4.

- *Sensitivity Analyses of the Endpoint*

The analyses will be repeated for subjects in the PPAS.

#### 7.6.5. Mean dB hearing threshold (AC over 9-16 kHz)

- *Computation of the Endpoint*

At each visit and by ear (left, right), the mean dB hearing threshold will be derived by averaging the AC audiometry dB hearing thresholds over 9-16 kHz frequencies. Left and right ears will be mapped to treated and untreated for analysis, as described in Section 3. Missing values will be imputed per Section 7.6.

- *Analysis of the Endpoint*

Descriptive summaries and treatment group comparisons will be performed for mean dB hearing threshold as described in Section 7.5.5.

- *Sensitivity Analyses of the Endpoint*

The analyses will be repeated for subjects in the PPAS.

If there are any dosing administrations errors such that a not qualified ear is treated, the descriptive summaries by treated and untreated ears will be repeated for subjects in the FAS including all treated and untreated ear data.

#### 7.6.6. Shift from no signal to any signal by frequency

- *Computation of the Endpoint*

For each frequency, shifts from no signal to any signal will be computed in subjects in the FAS with no signal (missing/imputed hearing response) at baseline in the treated ear. At each post-baseline visit, subjects with any signal (any non-missing/not imputed hearing response) in the treated ear will be flagged as 1 and as 0, otherwise. The endpoint will utilize imputed values per Section 7.6.

- *Analysis of the Endpoint*

For each frequency, the incidence of shifts from no signal at baseline to any signal at each post-baseline visit for treated ears will be summarized using frequencies and percentages by visit and treatment group for subjects with no signal at baseline in the FAS.

- *Sensitivity Analyses of the Endpoint*

The analyses will be repeated for subjects in the PPAS.

#### 7.6.7. Shift from no signal to any signal in two contiguous frequencies

- *Computation of the Endpoint*

Shifts from no signal in two contiguous frequencies at baseline to any signal in two contiguous frequencies at each post-baseline visit will be computed in subjects in the FAS with no signal (missing/imputed hearing response) at baseline in the treated ear for any two contiguous frequencies. At each post-baseline visit, subjects with any signal (any non-missing/not imputed hearing response) in the treated ear at the same two contiguous frequencies will be flagged as 1 and as 0, otherwise. The endpoint will utilize imputed values per Section 7.6.

- *Analysis of the Endpoint*

The incidence of shifts from no signal in two contiguous frequencies at baseline to any signal in two contiguous frequencies at each post-baseline visit for treated ears will be summarized using frequencies and percentages by visit and treatment group for subjects in the FAS with no signal in any two contiguous frequencies at baseline in the treated ear.

- *Sensitivity Analyses of the Endpoint*

The analyses will be repeated for subjects in the PPAS

#### 7.6.8. Shift from no signal to any signal in three contiguous frequencies

- *Computation of the Endpoint*

Shifts from no signal in three contiguous frequencies at baseline to any signal in three contiguous frequencies at each post-baseline visit will be computed in subjects in the FAS with no signal (missing/imputed hearing response) at baseline in the treated ear for any three contiguous frequencies. At each post-baseline visit, subjects with any signal (any non-missing/not imputed hearing response) in the treated ear in the same three contiguous frequencies will be flagged as 1 and as 0, otherwise. The endpoint will utilize imputed values per Section 7.6.

- *Analysis of the Endpoint*

The incidence of shifts from no signal in three contiguous frequencies at baseline to any signal in three contiguous frequencies at each post-baseline visit for treated ears will be summarized using frequencies and percentages by visit and treatment group for subjects in the FAS with no signal in three contiguous frequencies at baseline in the treated ear.

- *Sensitivity Analyses of the Endpoint*

The analyses will be repeated for subjects in the PPAS.

## 7.7. Tinnitus Functional Index

The TFI is a 25-item questionnaire that can be used to quantify the treatment-related change in tinnitus. The TFI includes individual item scores, a total score, and eight subscales addressing: the intrusiveness of tinnitus, the sense of control the patient has, cognitive interference, sleep disturbance, auditory issues, relaxation issues, quality of life, and emotional distress. All instrument items, except items 1 and 3, are on an inverted 0-10 scale with 0 being most favorable and 10 being least favorable. Items 1 and 3 are on an inverted 0% to 100% scale with 0% being most favorable and 100% being least favorable. The total score and individual subscale scores are the average item response (all subscales consist of 3 or 4 items) that is then scaled to 0-100. Detailed scoring instructions are in Section 14.3. The subject will complete the instrument (either directly onto the questionnaire in person, via web, or over the phone) at the Day 1, 60, 120, and 210 visits.

Baseline scores for analysis will be computed from the Day 1 visit. No imputation will be performed for missing data and Section 14.3 provides further detail regarding the impact of missing data on TFI scores. No sensitivity analyses will be performed for the TFI endpoints.

### 7.7.1. Mean total score, individual subscale scores, and loudness score

- *Computation of the Endpoint*

At each visit, the mean total TFI score and individual subscale scores will be computed per Section 14.3. The loudness score will be the response from item 2.

- *Analysis of the Endpoint*

The mean total TFI score, individual subscale scores, and loudness score will be summarized descriptively by visit and treatment group for subjects in the FAS.

For subjects in the FAS, treatment group comparisons for the mean total TFI score will be analyzed using a mixed-effect, repeated measures model using fixed covariates for treatment group, WR score at baseline (<50% versus ≥50%), etiology of hearing loss (SSNHL versus NIHL), visit, and interaction between visit and treatment group. As described in Section 7.3.4, separate models will be fit specifying UN and AR(1) covariance structures (implemented with a repeated statement in SAS). The covariance structure providing the lowest corrected AICc and BIC values from the model will be implemented for the TFI total score and all other TFI endpoints. The treatment group differences analyzed will be between each FX-322 group (including the pooled FX-322 group) versus placebo, and comparisons between the individual FX-322 groups (excluding the pooled FX-322 group). Comparisons will be made by visit (e.g., estimated LS Mean differences by visit) and overall (e.g., Type III Sums of Squares). The analysis will be repeated for the loudness score.

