**Study Population:**

Male and female adults (18 to 65 years inclusive), otherwise healthy with stable sensorineural hearing loss.

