### **8.4.2 Inclusion Criteria**

To be eligible for study entry subjects must satisfy all of the following criteria:

1. Subject has read and voluntarily signed the Informed Consent Form (ICF) after all questions have been answered and prior to any study-mandated procedure.
2. Adult aged 18-65 years inclusive.
3. Established diagnosis of stable sensorineural hearing loss by standard audiometric measures for  $\geq 6$  months prior to the Screening visit (no changes in air conduction greater than 10 dB at a single frequency or greater than 5dB at two contiguous frequencies from the prior audiogram to the Screening audiogram in the study ear).
4. Documented medical history consistent with hearing loss being caused by noise exposure or sudden sensorineural hearing loss (documented audiogram at least 6 months prior to screening required).
5. A pure tone average of 26-70 dB at 500Hz, 1000Hz, 2000Hz, and 4000Hz in the ear to be injected.
6. Subjects with a 15% - 85% correct score on Word Recognition test (8 – 42 words correct out of 50) at Screening in the study ear.
7. Ability to communicate well with the Investigator and is willing to comply with and complete all the study procedures.
8. Female subjects must be of non-childbearing potential or will need to utilize two methods of highly effective contraception during the study participation (e.g. hormonal contraception or an intrauterine device and condoms) or remain abstinent. Male subjects

should use condoms with spermicide during the course of the study or remain abstinent. Subjects should not donate sperm or ova during the study period.

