#### 4. ANALYSIS SAMPLES

The following definitions will be used to derive the analysis sets for this study.

- Full Analysis Set

The Full Analysis Set is defined as all randomized subjects who receive at least one dose of study drug (regardless of whether a full dose was administered) in the qualified ear per the

randomized treatment schedule. Subjects will be analyzed according to their randomized treatment group, as described in Section 3. For assessments completed by ear for each subject, treated (qualified) and untreated (not qualified) ears will be summarized separately, as described in Section 3. The FAS will be used to explore efficacy.

- Per Protocol Analysis Set

The Per Protocol Analysis Set is defined as subjects receiving all four doses of study drug or placebo in the qualified ear to be treated per the randomization treatment schedule and without major protocol deviations that could interfere with interpretation of the results. These major protocol deviations will be identified prior to breaking the study blind for the IA. Protocol deviations that occur after unblinding for the IA will be evaluated for major/minor classification by the blinded medical and study team prior to breaking the study blind for the CSR. If different from the FAS, the PPAS may be used in additional sensitivity analyses for efficacy. PPAS subjects will be analyzed according to their randomized treatment group, as described in Section 3. For assessments completed by ear for each subject, treated (qualified) and untreated (not qualified) ears will be summarized separately, as described in Section 3.

- Safety Analysis Set

The Safety Analysis Set will include all subjects exposed to study drug or placebo in any ear and will be analyzed according to the actual treatment group regardless of their randomized treatment assignment, as described in Section 3. For safety assessments by subject, the total number of FX-322 received in any ear will be used to assign actual treatment group. For safety assessments completed by ear for each subject, treated and untreated ears will be summarized separately, as described in Section 3. The SfAS will be used for the analysis of safety.

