#### 7.7.2. Change from baseline in mean total score, individual subscale scores, and loudness score

- *Computation of the Endpoint*

The change from baseline to each post-baseline visit will be computed as  $w - b$  where “w” is the post-baseline score and “b” is the score at baseline.

- *Analysis of the Endpoint*

The change from baseline to each post-baseline visit in mean total TFI score, individual subscale scores, and loudness score will be summarized descriptively by visit and treatment group for subjects in the FAS.

For subjects in the FAS, treatment group comparisons for the change from baseline in mean total TFI score will be analyzed using a mixed-effect, repeated measures model using fixed covariates for treatment group, WR score at baseline (<50% versus ≥50%), etiology of hearing loss (SSNHL versus NIHL), visit, and interaction between visit and treatment group. The covariance structure (UN or AR(1)) that provides the best model fit for the TFI total score, as described in Section 7.7.1, will be implemented with a repeated statement in SAS. The treatment group differences analyzed will be between each FX-322 group (including the pooled FX-322 group) versus placebo, and comparisons between the individual FX-322 groups (excluding the pooled FX-322 group). Comparisons will be made by visit (e.g., estimated LS Mean differences by visit) and overall (e.g., Type III Sums of Squares). The analysis will be repeated for the loudness score.

Correlation analyses between the mean change from baseline in total TFI score, individual subscale scores, and the loudness score versus the following WR, WIN and PTA continuous endpoints for treated ears will be performed for subjects in the FAS:

- WR:

- Percentage of recognized words (Section 7.3.2)
- Absolute percent change from baseline in word recognition (Section 7.3.3)
- Relative percent change from baseline in word recognition (Section 7.3.4)
- Arcsine-transformed word recognition (Section 7.3.6)
- WIN:
  - Percentage of recognized words (Section 7.4.2)
  - Absolute percent change from baseline in word recognition (Section 7.4.3)
  - Relative percent change from baseline in word recognition (Section 7.4.4)
  - Median Spearman-Kärber estimates of dB thresholds for word recognition (Section 7.4.6)
- PTA:
  - Mean overall PTA (AC over 0.5, 1, 2, and 4 kHz) (Section 7.5.5)

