The possible responses to items except 1 and 3 are 0, 1, 2, 3, 4, 5, 6, 7, 8, 9, and 10. The possible responses to items 1 and 3 are 0%, 10%, 20%, 30%, 40%, 50%, 60%, 70%, 80%, 90%, and 100%. Prior to computing the TFI total score, the responses for items 1 and 3 are transformed from a percentage scale to a 0 to 10 scale, by dividing the values by 10.

The TFI total score is then defined as a sum of the 25 items, after items 1 and 3 are transformed. The total TFI score is calculated as the sum of the 25 scores, divided by the number of non-missing scores, multiplied by 10. The total score ranges from 0 to 100, with higher scores representing greater perceived handicap.

The TFI total score is not valid if 7 or more items are omitted. To be valid as a measure of tinnitus severity, at least 19 items must be completed.

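### SAP 7.7 analyses the TFI in the whole FAS although tinnitus is not an entry criterion, so the reported effect is scaled by an unstated share of subjects with tinnitus

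*SAP*

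**What the plan says.** **Who enters.** Protocol 8.4.2 opens with "To be eligible for study entry subjects must satisfy all of the following criteria". The eight criteria cover consent, age, stable hearing loss, etiology ("Documented medical history consistent with hearing loss being caused by noise exposure or sudden sensorineural hearing loss"), pure tone average, word recognition, ability to comply and contraception. None of the sixteen exclusions in 8.4.3 mentions tinnitus. The synopsis describes the population as "Male and female adults (18 to 65 years inclusive), otherwise healthy with stable sensorineural hearing loss".

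**Who is analysed.** SAP 4: "The Full Analysis Set is defined as all randomized subjects who receive at least one dose of study drug", with the added condition that the dose went into the qualified ear. Tinnitus plays no part.

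**How the TFI is analysed.** SAP 7.7 introduces it thus: "The TFI is a 25-item questionnaire that can be used to quantify the treatment-related change in tinnitus". SAP 7.7.1 models the total and loudness scores as levels: "For subjects in the FAS, treatment group comparisons for the mean total TFI score will be analyzed". SAP 7.7.2 does the same for change: "For subjects in the FAS, treatment group comparisons for the change from baseline in mean total TFI score will be analyzed", and adds correlations with WR, WIN and PTA by visit and treatment group. The model terms are treatment, WR stratum, etiology, visit and the visit-by-treatment interaction. Day 1 TFI is not among them. SAP 7.7 rules out TFI sensitivity analyses, and SAP 7.10 plans subgroups only for WR and WIN.

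**The scale.** SAP 14.3: "The total score ranges from 0 to 100, with higher scores representing greater perceived handicap". The total is invalid when 7 or more of the 25 items are omitted. Nothing says how a subject without tinnitus should be scored.

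**The concern.** Every TFI item asks about the subject's own tinnitus. A subject without it either scores at or near 0, the best possible value, or leaves items blank. Someone at 0 can only stay there or worsen. Averaging such subjects with those who can improve gives a number that mixes two things: how much tinnitus changed in those who had it, and how many had it. The second is not stated, and no planned table separates them.

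What is at stake is how an exploratory result is read. A small FAS difference could mean a weak effect on tinnitus, or a useful effect in a minority. Subjects fixed at zero change also enter the planned correlations and tell us nothing about how tinnitus moves with hearing; the size of that effect is not quantified here. In the level model of 7.7.1, with no Day 1 TFI term, a chance difference between arms in the share with tinnitus adds noise to the treatment contrast.

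**Working it through.** The documents give no TFI effect, SD or tinnitus prevalence, and SAP 2.4 says the sample size had no formal statistical basis. There is therefore no planned figure to reproduce. From the documents come 24 subjects per arm and a 0–100 scale with 0 best. All other inputs below are assumptions.

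**1. Dilution.** Let p be the share with tinnitus on Day 1 and D the treatment effect in them. If the rest score 0 and stay at 0 in both arms, the FAS difference is p × D. With D = 10:

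| p | FAS difference |
|---|---|
| 0.4 | 4 |
| 0.6 | 6 |
| 0.8 | 8 |
| 1.0 | 10 |

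**2. Blank forms.** If a fraction b of tinnitus-free subjects leave the form blank, their totals are invalid and they drop out. The effective share becomes p / [p + (1 − p)(1 − b)]. At p = 0.6 and b = 0.5 this is 0.6/0.8 = 0.75, so a 10-point effect reads as 7.5. At b = 1 it reads as 10. A subject blank on Day 1 who completes the form later would enter the level model but not the change model.

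**3. Chance imbalance in the level model (7.7.1 only).** The SD of the between-arm difference in the share with tinnitus is √[2p(1 − p)/24]: 0.141 at p = 0.4 or 0.6, and 0.115 at p = 0.8. With an assumed mean TFI of 40 in those with tinnitus, this alone contributes 5.7 and 4.6 points.

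Restricting to the subset does not remove chance imbalance. With an assumed score SD of 22 and p = 0.6, the SD of the chance Day 1 difference between arms is:
- FAS: √[2 × (0.6 × 22² + 0.24 × 40²)/24] = √(2 × 674.4/24) = 7.5 points.
- Subset, 0.6 × 24 = 14.4 per arm: 22 × √(2/14.4) = 8.2 points.

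The tool for this is the Day 1 covariate.

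**4. Power, FAS against subset.** Assumptions: D = 13, SD of change 20, Day 1 mean 40, score SD 22, placebo change −5, 24 per arm, two-sided 0.05, normal approximation. The FAS per-subject variance is p × SD² + p(1 − p) × m², where m is the arm mean among subjects with tinnitus (change: −5 and −18; level: 35 and 22).

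For the change score at p = 0.6, the variances are 240 + 0.24 × 25 = 246 (placebo) and 240 + 0.24 × 324 = 317.8 (active). SE = √(563.8/24) = 4.85, the difference is 7.8, and power is Φ(7.8/4.85 − 1.96) = 36%. In the subset, SE = 20 × √(2/14.4) = 7.45, and power is Φ(13/7.45 − 1.96) = 42% (41.5% before rounding).

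| p | Change: FAS / subset | Level: FAS / subset |
|---|---|---|
| 0.8 | 49% / 52% | 35% / 45% |
| 0.6 | 36% / 42% | 23% / 35% |
| 0.4 | 24% / 30% | 15% / 25% |

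For the change score the subset gains only about 3 to 6 points, because stable zeros reduce the variance as well as the effect.

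**5. Price of the subset.** At p = 0.4 it holds about 10 per arm. The approximate 95% interval around a correlation of 0, tanh[1.96/√(n − 3)], widens from ±0.40 at n = 24 to ±0.63 at n = 10.

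**The case against.** The FAS contrast is a valid randomised estimate for the enrolled population. The TFI is an additional exploratory endpoint, p-values are descriptive (SAP 7.1.4), and no stated decision depends on it. Day 1 TFI scores will be summarised by group, so a gross imbalance would be seen, and SAP 1 allows labelled post hoc analyses. If nearly all subjects have tinnitus, nothing is lost. All of this stands, and it limits the point to interpretation. It does not supply the missing estimate, and a cut-off chosen after unblinding would carry less weight than one fixed before.

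Two stronger readings are tempting.

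- A reader might infer that new-onset tinnitus goes unseen as a safety signal. The documents do not support this. SAP 8.3 tabulates new or worsened events by preferred term, and ear-related events by treated and untreated ear, which the TFI cannot distinguish. That route relies on a non-leading question (Protocol 13), and tinnitus is not an event of special interest, so a TFI tabulation could add to it. Only the TFI mean averages relief against onset. In an extreme assumed case (40% with tinnitus, 13 points of relief, 20% of the others developing tinnitus at a score of 40), the net is −0.4 × 13 + 0.6 × 0.2 × 40 = −0.4.
- A reader might take the 4.6 to 5.7 points of chance imbalance as noise in the protocol endpoint. That endpoint is mean change, in which stable zeros contribute nothing. The figure concerns only the level model of 7.7.1.

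Subsetting does not break the randomised comparison: Protocol 10.1.2 places the TFI before randomisation. The SAP already restricts denominators by baseline status in 7.6.6 to 7.6.8.

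**Conclusion.** The point holds as a limit on interpretation. As planned, the TFI difference in the FAS is the effect in subjects with tinnitus scaled by a share that the documents do not give. At an assumed share of 40% to 100%, a 10-point effect would read as 4 to 10 points. This assumes that tinnitus-free subjects complete the form, score 0 and stay there. It shrinks towards nothing if nearly all subjects have tinnitus or if those without it leave the form blank.

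For the change model the gain from a subset is mainly a readable estimate; the power gain is small under the assumptions shown. For the level model the omission of Day 1 TFI matters more. The documents support neither a claim that the FAS analysis is invalid nor one that a harm signal is concealed.

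**What to change.** Amend SAP 7.7.1 and 7.7.2 before unblinding. The Day 90 interim unblinding is the relevant one, since SAP 10 lists the TFI among its outputs.

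1. Keep the all-FAS analyses.
2. Add the TFI total and loudness models, change summaries and correlations in FAS subjects with tinnitus on Day 1. Use one pre-set definition, for example Day 1 item 2 (loudness) above 0, and state how a tinnitus-free subject is scored and how a blank Day 1 form is classified.
3. Add the Day 1 score as a covariate in the TFI models, with Day 1 not also among the modelled visits. This deals with chance baseline imbalance in 7.7.1 and fits Protocol 14.1.5, which foresees baseline adjustment where appropriate.
4. As a supplement to the adverse event tables, tabulate by arm the subjects without Day 1 tinnitus who later exceed a pre-set TFI threshold. Any score above 0 is too loose: one point on one of 25 items gives 1/25 × 10 = 0.4 and would count a stray response.

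The cost is SAP wording and one further set of TFI tables, with no new data. The subset will be smaller than 24 per arm unless every subject has tinnitus, so per-arm correlations will be less precise.
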